4.8 Additional Exploratory Endpoints

[REDACTED]

[REDACTED]

[REDACTED]

[REDACTED]

[REDACTED]

[REDACTED]

5 INTERIM ANALYSIS

An interim analysis will occur after approximately 50% of the subjects have had the opportunity to complete the Week 78 visit for both 221AD301 and 221AD302. To maintain the integrity of the study in the event of the interim analysis, an independent group external to Biogen that will not be involved in the conduct of the study after unblinding will perform the interim analysis. The IDMC will review the unblinded results of the interim analysis provided by the independent group and will make a recommendation to Biogen based on pre-specified criteria.

An interim analysis for futility of the primary endpoint will be performed to allow early termination of the studies if it is evident that the efficacy of aducanumab is unlikely to be achieved. The futility criteria will be based on conditional power, which is the chance that the primary efficacy endpoint analysis will be statistically significant in favor of aducanumab at the planned final analysis, given the data at the interim analysis. The conditional power is calculated assuming that the future unobserved effect is equal to the maximum likelihood estimate of what is observed in the interim data:

$$CP(Z(1) \geq Z_\alpha | Z(t)) = 1 - \Phi \left(\frac{Z_\alpha \sqrt{n_2} - Z(t)\sqrt{n_1}}{\sqrt{n_2 - n_1}} - \frac{Z(t)\sqrt{n_2 - n_1}}{\sqrt{n_1}} \right)$$

where t is the fraction of information and $Z(t)$ is the observed Z-statistic at the interim analysis, $Z(1)$ is the Z-statistic and α is the type I error at the final analysis, n_1 and n_2 are the number of subjects at the interim and at the final analysis, respectively.

The futility decision will primarily be based on the conditional power for the primary efficacy endpoint. The study will not be considered as futile unless both studies 221AD301 and 221AD302 have conditional power for the primary efficacy endpoint less than 20% in both the high-dose and low-dose treatment groups. Given the insufficient knowledge of aducanumab's potential effects on various functional/cognition endpoints or in certain subgroups at the present time, other data in addition to the pre-specified futility criteria will be considered as well, and the IDMC may recommend the studies to be continued as planned based on the weight of the evidence.

An interim analysis for superiority may be performed, to allow the possibility to demonstrate the treatment effect early. If an interim analysis for superiority is performed, the O'Brien-Fleming stopping boundary will be used. If an interim analysis for superiority is not performed, then no alpha adjustment will be used for the final analysis after all subjects have had the chance to complete the Week 78 visit.

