3 SAMPLE SIZE JUSTIFICATION

The study's sample size is based, in part, on results from a protocol-specified interim analysis from Study 221AD103 which included 1 year data from 1, 3 and 10 mg/kg treatment groups.

A sample size of 450 subjects per treatment group (1350 in total) was planned to have approximately 90% power to detect a true mean difference of 0.5 in change from baseline CDR-SB at Week 78 between the 2 treatment groups. This power calculation was based on a 2-sided t-test assuming equal variance with a final significance level of 0.05, a standard deviation (SD) of 1.92 and a drop-out rate of 30%. The SD estimate of 1.92 for Week 78 reflected a 39% increase over the SD from the protocol-specified interim analysis of 1-year data.

The assumed true mean difference of 0.5 between the 2 treatment groups represents an approximately 25% reduction in the placebo mean change from baseline at Week 78 if the placebo mean change is estimated to be 2.

As defined in the protocol, the sample size for this study (and for the identically designed Study 221AD301) was reassessed in a blinded manner in November 2017 (approximately 3 months before enrollment completion and with about 10.6% of the data available on the primary endpoint from Studies 221AD301 and 221AD302 combined). At this timepoint, the SD of the primary endpoint was estimated based on the pooled blinded data from two studies using a modified version of Gould-Shih simple-adjustment one sample variance (Zucker et al. 1999):

$$s_{adj}^2 = s_{os}^2 - \frac{2N}{9(N-1)} \delta^2,$$

where N denotes the number of subjects included in the analysis for blinded sample size re-estimation (subjects with both baseline and Week 78 CDR-SB available at the time of sample size re-estimation), δ is the assumed true treatment effect (same treatment effect assumed for both the high dose group and low dose group in this analysis), and s_{os}^2 is the unadjusted one sample variance of the primary endpoint estimate from the pooled blinded data.

As a result of this analysis, the sample size has been increased from 1350 to 1605 (450 to 535 per treatment group) to assure adequate power for detecting a mean treatment effect of 0.5.

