4 STATISTICAL ANALYSIS METHODS

4.1 General Considerations

This statistical analysis plan (SAP) only covers the analyses for the primary, secondary and tertiary objectives for the placebo-controlled portion of the study. Hereafter, the placebo-controlled portion of the study will be referred to as “the study” in the rest of this SAP (e.g.,

CONFIDENTIAL

The information contained herein may not be used, disclosed, or published without the written consent of Biogen MA Inc.

	Statistical Analysis Plan Placebo-Controlled Period	Final V1.0
---	---	-------------------

completion of the study means completion of the placebo-controlled portion). A separate SAP will be prepared for the analyses of the LTE period and integrated analyses across both portions of the study. The analyses of additional exploratory endpoints will be documented separately.

Summary tables will be presented using descriptive summary statistics. For continuous variables, summary statistics will generally include: number of subjects with data, mean, standard deviation, median, 25% percentile, 75% percentile, minimum and maximum. For categorical variables, this will generally include: number of subjects randomized or dosed, number with data, and the percent of those with data in each category.

There are two types of analysis displays for tables: by treatment group (analysis display A in Appendix 6.1) and by treatment group stratified by ApoE status (analysis display B in Appendix 6.1; here ApoE status refers to the status recorded in IXRS [see Table 1 for correspondence between treatment groups and treatment groups stratified by ApoE status]). The analysis display for each analysis will be defined in each section. All the listings will be presented by treatment group stratified by ApoE status, unless otherwise specified.

Unless otherwise specified, baseline value is defined as the most recent non-missing measurement collected prior to the first dose. Change from baseline will be defined as post-baseline value minus baseline value.

Unless stated otherwise, all statistical tests will be 2-sided with statistical significance level of 0.05.

The statistical software, SAS® will be used for all summaries and analyses.

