4.3.2 Primary Efficacy Endpoint

4.3.2.1 Primary analysis

The estimand of the primary analysis is the mean difference of the change from baseline CDR-SB scores at Week 78 between treatment groups in the ITT population [ICH E9 (R1) Addendum 2014, 2017]. All observed data will be included in the primary analysis, including data collected after intercurrent events [ICH E9 (R1) Addendum 2017], i.e., treatment discontinuation or a change in concomitant use of AD symptomatic medication.

The change from baseline CDR-SB scores will be summarized by treatment group at each post-baseline visit. A mixed model repeated measures (MMRM) model will be used as the primary analysis to analyze change from baseline CDR-SB using fixed effects of treatment group, time (categorical), treatment group-by-time interaction, baseline CDR-SB, baseline CDR-SB by time interaction, baseline MMSE, AD symptomatic medication use at baseline (yes/no; see Section 4.2.3 for definition of AD symptomatic medication use at baseline),

CONFIDENTIAL

The information contained herein may not be used, disclosed, or published without the written consent of Biogen MA Inc.

region, and laboratory ApoE ϵ 4 status (carrier/non-carrier). An unstructured covariance matrix will be used to model the within-patient variance-covariance errors. If the unstructured covariance structure matrix results in a lack of convergence, the heterogeneous Toeplitz covariance structure followed by the heterogeneous first-order autoregressive covariance structure will be used. The Kenward-Roger approximation will be used to estimate the denominator degrees of freedom. In the primary analysis, missing data are assumed to be missing at random [Rubin 1976].

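### The futility formula in SAP Section 5 leaves its critical value ambiguous and weights by subject counts instead of Week 78 information, so a computed 20% conditional power may not be 20%

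*SAP*

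**What the plan says.** SAP Section 5 plans a futility analysis once about half the subjects have had the chance to reach Week 78. Conditional power is the probability that Z(1) is at least Z_α given the interim Z(t), with the interim estimate assumed to hold for the remaining data. On the critical value the section says only that "α is the type I error at the final analysis"; it gives no number and no sidedness. On the weights it says that "n_1 and n_2 are the number of subjects at the interim and at the final analysis, respectively". An information fraction t is named, but it appears only as the argument of Z(t). Futility is not considered unless both studies have "conditional power for the primary efficacy endpoint less than 20% in both the high-dose and low-dose treatment groups".

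Elsewhere the level is stated plainly. Section 4.1 says that, unless stated otherwise, "all statistical tests will be 2-sided with statistical significance level of 0.05", and Section 3 sizes the study on "a 2-sided t-test assuming equal variance with a final significance level of 0.05". Section 5 adds that α is not adjusted at the final analysis unless a superiority interim is performed, in which case an O'Brien-Fleming boundary applies.

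The primary model (Section 4.3.2.1) is an MMRM over Weeks 26, 50 and 78, and "All observed data will be included in the primary analysis".

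**The concern.** An upper-tail event written with Z_α takes the upper α point of the normal distribution. Putting in the SAP's only α, 0.05, gives 1.645. A two-sided 0.05 test that succeeds in favour of aducanumab needs 1.960. A programmer who follows the text literally would compute the chance of passing an easier test than the planned one.

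The weights raise a second question. In an MMRM, subjects who have reached only Week 26 or Week 50 add some information about the Week 78 contrast: more than none, less than a subject with Week 78 data. No count of subjects reproduces that, and Section 5 does not say which subjects n1 and n2 count.

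This number is the main input to a stop-or-continue recommendation for two studies. The independent group that computes it would have to settle both matters itself, with unblinded data in hand.

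**Working it through.** **Which final test is planned.** Inputs from Section 3: difference 0.5, SD 1.92, 90% power, 30% dropout, 450 per group.
- Two-sided 0.05: n = 2 × (1.960 + 1.282)² × 1.92² / 0.5² = 310 evaluable per group, and 310 / 0.7 = 443, close to 450. With 450 × 0.7 = 315 evaluable, power is 0.905.
- One-sided 0.05: 253 evaluable, 362 after dropout, and power 0.948 at 315.

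Only the two-sided version reproduces the plan, so success at the final analysis needs Z ≥ 1.960.

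**The formula.** With f = n1/n2, the printed expression simplifies to

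CP = 1 − Φ[(c − Z/√f) / √(1 − f)],

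where c is the critical value. The algebra in Section 5 is correct. Setting CP = 0.20 gives the cut-off Z = √f × (c − 0.842 × √(1 − f)).

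**Effect of the critical value at f = 0.5.**
- c = 1.645: Z = 0.707 × (1.645 − 0.842 × 0.707) = 0.742.
- c = 1.960: Z = 0.707 × (1.960 − 0.842 × 0.707) = 0.965.
- At Z = 0.742, CP against 1.960 is 1 − Φ[(1.960 − 1.050) / 0.707] = 1 − Φ(1.287) = 9.9%.
- At Z = 0.965, the literal formula would show 34.6%.

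For an interim Z between 0.742 and 0.965, the two readings give opposite answers for that comparison. The 9.9% depends on f: it is 10.9% at f = 0.35 and 7.8% at f = 0.70. With an O'Brien-Fleming final value (assumed 1.97 to 1.98) it would be about 9.5 to 9.7%.

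On the CDR-SB scale, assuming SD 1.92 and 30% dropout, the standard error at half information is 1.92 × √(2 / (0.5 × 0.7 × N)). For N = 535 per group the cut-offs are about 0.15 and 0.19 points; for N = 450 they are about 0.16 and 0.21. The SAP does not give the re-estimated SD, so these figures are illustrative.

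**Effect of the weights.** The SAP gives neither the correlation between visits nor the share of subjects with partial data at the interim. Assumptions: half the subjects have full information; a further share q (0.2 to 0.4) have only earlier visits; the correlation ρ between the earlier data and Week 78 is 0.5 to 0.8; dropout is similar at both analyses and cancels. With this simple two-stage approximation, the information fraction for the Week 78 mean is

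t = 1 / [(1 − ρ²)/0.5 + ρ²/(0.5 + q)].

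- ρ = 0.5, q = 0.2: t = 1 / (0.75/0.5 + 0.25/0.7) = 0.54.
- ρ = 0.8, q = 0.4: t = 1 / (0.36/0.5 + 0.64/0.9) = 0.70.

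Take Z = 0.965, where a count ratio of 0.5 with c = 1.960 shows 20%. Conditional power is 17.1% at the first t and 7.1% at the second.

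**Counting everyone with any data instead.** The ratio becomes 0.5 + q, which is 0.7 or 0.9, against a t of 0.54 or 0.70. At the same Z = 0.965 the formula shows 7.1% where the value is 17.1%, or about 0.1% where it is 7.1%. This count understates conditional power and makes stopping easier.

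**The case against.** A reader might infer that the 20% threshold is in fact a 10% threshold. The SAP does not support that. Section 5 gives α no number, and under the null hypothesis a one-directional event Z(1) ≥ Z_α has probability α, which for a two-sided 0.05 test is 0.025. Section 5 also describes the target in words, as final significance in aducanumab's favour, which with Section 4.1 points to 1.960. On that reading 20% is 20% at half information. The 9.9% therefore holds only if 1.645 is actually used. The SAP prints no conditional-power figure that could be called miscalculated.

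A reader might also infer that the result swings widely with how n1 is counted. Section 5 times both analyses by the opportunity to complete Week 78, and counting both on that basis, or both as completers, gives a ratio near 0.5. Large swings need mismatched bases or the counting of subjects without Week 78 data. What survives is narrower: even consistent counting omits the partial-visit information. Section 5 does not define the interim dataset, so this presumes that the interim Z comes from the primary MMRM.

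Nor does the literal reading threaten patients with a wrongful stop. It overstates conditional power, so stopping is harder, and it leaves the final test and its type I error untouched. The direction of Z can be inferred from the wording about favouring aducanumab; stating it is tidiness. Finally, all four conditional powers must be below 20%, and the IDMC may recommend continuing on the weight of the evidence.

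**Conclusion.** The point holds as an ambiguity in a decision rule, with two parts.

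1. Critical value: computed as written, the nominal 20% rule at n1/n2 = 0.5 stops only below Z = 0.742, where conditional power for the planned test is 9.9%, instead of below Z = 0.965. If one-sided 0.025 was intended, the rule is right and the notation alone needs correcting.
2. Weights: a ratio of 0.5 counted by opportunity to reach Week 78 understates the information fraction, which is about 0.54 to 0.70 under the assumed correlations and partial-data shares. A computed 20% is then about 17% down to 7%. This part remains even with 1.960. Counting everyone with any data errs in the opposite direction.

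The first part rests on the literal reading of α. The second rests on assumed inputs and on the interim Z coming from the primary MMRM. Should-fix: the number is the main futility criterion, but four conditions must hold together and the IDMC keeps discretion.

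**What to change.** In Section 5:
- Replace Z_α by Z_(α/2) = 1.960 with α = 0.05 two-sided, or by the final O'Brien-Fleming critical value if a superiority look is taken.
- Replace n1/n2 by t = I1/I2, where I = 1/SE² of the Week 78 treatment contrast from the MMRM, I1 is observed at the interim and I2 is projected for the final analysis. State how I2 is projected.
- State that Z is signed so that positive values favour aducanumab (placebo minus aducanumab on CDR-SB change).

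The cost is a few lines of SAP text, matching wording in any document that governs the interim analysis, and a small change to the program. It should be done before any unblinded interim data are seen. No further data collection is needed, and the final analysis is unaffected.

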6 APPENDIX

6.1 Analysis Display

Analysis display A

Placebo	BIIB037 low dose	BIIB037 high dose
---------	------------------	-------------------

Analysis display B

Placebo			BIIB037 low dose			BIIB037 high dose		
ApoE ε4+ placebo	ApoE ε4- placebo	Total	ApoE ε4+ 3 mg/kg	ApoE ε4- 6 mg/kg	Total	ApoE ε4+ 10 mg/kg	ApoE ε4- 10 mg/kg	Total

6.2 Protocol Deviation Classification

Deviation Category	Deviation Description	Severity Classification
Administrative criteria	Study team member performing study assessments without being authorized as per delegation log.	Minor
Administrative criteria	Unblinded information made available to the blinded CRA.	Major
Administrative criteria	Unblinded information made available to the blinded site personnel.	Major
Administrative criteria	Incorrect version of any assessments used	case by case
Administrative criteria	Filing issues misfiling of documents	N/A
Administrative criteria	Correction of source data not compliant with GCP	N/A
Administrative criteria	Sharing of account credentials between raters on the MedAvante Virgil tablet/Portal, or sharing of accounts on any study system	Major
Concomitant Medications	Administration of any vaccination/booster should be given < 10 days prior to any dosing visit or 10 days after a dosing visit.	Minor
Concomitant Medications	Administration of any disallowed concomitant therapy to the subject.	Major
Concomitant Medications	Change of medications that subjects were receiving at enrollment or start of new medications or herbal preparations during the study period, without consultation with the investigator and review with the Medical Monitor	Case by case basis
Concomitant Medications	Change in AD medications during course of the study.	Minor
Eligibility and Entry criteria	Any "no" response to inclusion criteria and/or any "yes" response to exclusion criteria and subject was subsequently randomized for criteria.	Major
Eligibility and Entry criteria	Any eligibility assessment not performed.	Major
Eligibility and Entry criteria	Any eligibility assessment performed after the randomization of the patient (including lab samples), and subject is ineligible based upon assessment.	Major
Eligibility and Entry Criteria	Exclusionary lab value results but subject was dosed.	Major
Eligibility and Entry criteria	Subject not eligible based on scores of CDR, MMSE, RBANS DMI, as defined by inclusion criterion #6.	Major
Eligibility and Entry criteria	Subject on allowed chronic medications that have not been stable for at least 4 weeks prior to Screening V1 or use of AD medications at doses that have not been stable for at least 8 weeks prior to Screening V1.	Major

CONFIDENTIAL

The information contained herein may not be used, disclosed, or published without the written consent of Biogen MA Inc.

	Statistical Analysis Plan Placebo-Controlled Period	Final V1.0
---	--	-------------------

Informed Consent	Subject/informant/legally authorized representative did not sign Main ICF, PET ICF, and/or Substudy ICFs (and substudy procedures were conducted). Not clear on the ICF who has been signing the document (patient or legal representative).	Major
Informed Consent	Principal Investigator / individual obtaining consent did not sign Main ICF, PET ICF, and/or Substudy ICFs (and substudy procedures were conducted).	Major
Informed Consent	Not clear on the the ICF who has been signing the document (patient or legally authorized representative).	Major
Informed Consent	ICF signed by either only patient or only care giver/legally authorized representative, when ICF should have been signed by both.	Major
Informed Consent	Incorrect or outdated version of Main ICF, PET ICF, and/or Substudy ICFs signed by subject/informant/legally authorized representative.	Major
Informed Consent	IEC/IRB contact details or site's contact details not included on ICF.	Minor
Informed Consent	Incorrect completion of ICF (i.e., subject/study partner/LAR/person obtaining consent did not provide date of signature; subject/study partner/LAR/person obtaining consent noted incorrect date of signature; subject/study partner/LAR/person obtaining consent printed name when should have signed, subject/study partner/LAR/person obtaining consent signed on line for printed name, printed name on line for signature, etc.)	Minor
Informed Consent	Site personnel who signed ICF is not on Site Personnel Signature Delegation Log and/or not authorized by PI to sign ICF	Major
Informed Consent	No evidence (source documentation) that Informed Consent was obtained from the study subject / study partner.	Major
Informed Consent	ICF obtained by subject is not in subject's native language.	Major
Informed Consent	Protocol specific procedures such as physical exam, medical history, neurological history, ECGs, rater scales, lab tests, blood draws, including first study drug dose performed prior to the date of the consent.	Major
Informed Consent	Subject and/or Study Partner/Caregiver not signing ICFs at time of re-consent.	Major
Informed Consent	Untimely re-consenting of subject/caregiver on newly approved ICFs.	Major
Investigational Product Compliance	IP storage temperature out of range and site used IP without confirmation from Biogen regarding usability	Case by case basis
Investigational Product Compliance	Incorrect cohort IP dispensed to subject	Major
Investigational Product Compliance	IP is not stored in blinded manner.	Major
Investigational Product Compliance	Unblinded pharmacist discarded/destroyed used IP vial prior to IP accountability being conducted by unblinded CRA and without previous approval.	case by case basis
Investigational Product Compliance	IP temperature log is not being maintained nor checked by the unblinded pharmacist.	Major
Investigational Product Compliance	Non-compliant with IP usage according to DHA (note: this does not include deviation regarding removing overfill on saline bag)	Major
Investigational Product Compliance	Dosing based on weight calculation is inaccurate (i.e., discrepancies between Weight Communication Form and IXRS entry, ratio not respected when preparing dose, etc.)	Major
Investigational Product Compliance	Overdose of IP occurs.	Major
Investigational Product Compliance	Overdose Form not faxed to Quintiles Lifecycle Safety within 24 hours of site being made aware of an overdose.	Major
Investigational Product Compliance	Titration schedule not respected when dosing subject.	Major
Investigational Product Compliance	Down-dosing / discontinuation of dosing not respected by the unblinded pharmacist following ARIA-H and ARIA-E cases, as prescribed by the protocol, investigator, Medical Monitor, and/or sponsor.	Major

CONFIDENTIAL

The information contained herein may not be used, disclosed, or published without the written consent of Biogen MA Inc.

	Statistical Analysis Plan Placebo-Controlled Period	Final V1.0
---	--	-------------------

Investigational Product Compliance	Missed infusion visit (not due to temporary discontinuation of dosing as prescribed by the protocol, investigator, Medical Monitor, and/or sponsor due to ARIA-H or ARIA-E case).	case by casis
Investigational Product Compliance	IP storage temperature out of range (2-8 °C).	Minor
Investigational Product Compliance	Administration of expired IP.	Major
Investigational Product Compliance	IP rounding discrepancies not in accordance with the Directions for Handling & Administration document (DHA).	Minor
Investigational Product Compliance	Administration of IP that was rejected after a temperature excursion.	Major
Investigational Product Compliance	IP administered in less than 21 days.	Minor
Laboratory assessments criteria	Ambient samples received at central laboratory that should have been shipped frozen.	Minor
Laboratory assessments criteria	Frozen samples received at central laboratory that should have been shipped ambient.	Minor
Laboratory assessments criteria	Lab samples not drawn, or results unavailable.	Minor
Laboratory assessments criteria	Laboratory results not acknowledged by PI, or medically qualified and delegated study personnel.	case by case
Laboratory assessments criteria	Pre-dose and/or post-dose PK samples not collected, or not collected within protocol specified time.	Minor
Laboratory assessments criteria	CSF cell counts and differentials not sent to local laboratory for analysis (for subjects participating within CSF substudy).	Minor
Laboratory assessments criteria	Lab specimens temperature log is not being maintained nor checked by applicable study personnel.	Major
Laboratory assessments criteria	Use of incorrect lab kit.	Minor
Laboratory assessments criteria	PBMC not collected, or not collected within protocol specified time.	Minor
Other	Site repeatedly commits same minor deviations.	Major
Randomization criteria	Subject recorded as randomized in IXRS by mistake but not dosed.	Major
Randomization criteria	Subject randomized to wrong arm due to mis-entry of ApoE ε4 carrier status.	Major
Regulatory or Ethics Approval Criteria	No evidence that IRB / CEC / LEC approved the final protocol.	Major
Regulatory or Ethics Approval Criteria	No evidence that IRB / CEC / LEC was notified of protocol amendments in a timely manner.	Minor
Regulatory or Ethics Approval Criteria	Failure to notify or obtain approval from the IRB / CEC / LEC of a change of investigator.	Minor
Regulatory or Ethics Approval Criteria	Failure to obtain or keep updated regulatory authorization to conduct a study.	Major
Regulatory or Ethics Approval Criteria	Failure to obtain IRB / CEC / LEC approval of a subject directed document (e.g., subject questionnaires, advertisements, etc.)	Major
Regulatory or Ethics Approval Criteria	Failure in Safety Reporting as per local requirements (SUSARS, line listings, progress reports, etc.)	Minor
Serious Adverse Event Criteria	SAEs not appropriately reported (i.e., reported as an AE when SAE criteria have been met, or SAE not reported within 24 hours).	Major
Serious Adverse Event Criteria	Pregnancies not appropriately reported within 24 hours of study site staff becoming aware of the pregnancy.	Major
Serious Adverse Event Criteria	Adverse Events of Special Interest not reported within 72 hours following the receipt of abnormal MRI findings from the central MRI reader.	Major
Serious Adverse Event Criteria	SAEs not appropriately reported to the IRB/EC.	Minor
Study Procedures criteria	Inconsistent rater used for primary, secondary endpoints	Major

CONFIDENTIAL

The information contained herein may not be used, disclosed, or published without the written consent of Biogen MA Inc.

Study Procedures criteria	CDR raters were performing other assessments on subjects they performed CDRs for.	Major
Study Procedures criteria	Secondary endpoint assessments raters were performing other assessments on subjects they performed these assessments for.	Major
Study Procedures criteria	MOCA was administered by a rater rather than the treating HCP.	Major
Study Procedures criteria	Assessment performed by non-qualified rater	Major
Study Procedures criteria	Any eligibility criteria not confirmed prior to dosing, but deemed eligible post-randomization (including verification of eligibility based on cancer criteria with Medical Monitor [inclusion criterion #10]).	Minor
Study Procedures criteria	MRI and/or PET scan being conducted as part of Screening Visit 2 or Screening Visit 3 procedures without PI verification of eligibility at Screening Visit 1 (including laboratory and cognitive assessment eligibility) without permission of the sponsor/Medical Monitor. Please note that ApoE ε4 results are not necessary to move onto Screening Visits 2 or 3.	Minor
Study Procedures criteria	PET scan being conducted as part of Screening Visit 3 prior to MRI central read confirming eligibility at Screening Visit 2, without permission of the sponsor/Medical Monitor.	Minor
Study Procedures criteria	Dose reduction administered by PI/sub-I when protocol requires return to last dose following temporary discontinuation of IP following ARIA event under Protocol v. 3.	case by case
Study Procedures criteria	██████████ was not administered.	Minor
Study Procedures criteria	Primary endpoint assessment not conducted or administered at a study visit, as per protocol. Please note that deviation will not apply for any cognitive assessments that were not administered or completed, due to subject's decline in cognition.	Major
Study Procedures criteria	Secondary endpoint assessments not conducted or administered at a study visit, as per protocol. Please note that deviation will not apply for any cognitive assessments that were not administered or completed, due to subject's decline in cognition.	Major
Study Procedures criteria	Tertiary endpoint efficacy assessments (with the exception of the ██████████ and ██████████) not conducted or administered at a study visit, as per protocol. Please note that deviation will not apply for any cognitive assessments that were not administered or completed, due to subject's decline in cognition.	Minor
Study Procedures criteria	C-SSRS not conducted or administered at a study visit, as per protocol.	Minor
Study Procedures criteria	Systolic blood pressure, diastolic blood pressure, heart rate, body temperature, and/or respiratory rate not assessed as part of vital signs, or vital signs not measured with the subject supine and/or after the subject has been resting for at least 10 minutes.	Minor
Study Procedures criteria	Serum pregnancy test not conducted at Screening Visit 1, or urine pregnancy test not conducted at applicable study visits for subjects of child-bearing potential.	Major
Study Procedures criteria	MRI and/or PET scan being conducted on subsequent subjects should site not receive passing QC report on first in-vivo scan.	Minor
Study Procedures criteria	ARIA management not being followed as per protocol specifications.	Major
Study Procedures criteria	Non-IEC/IRB approved document(s) dispensed to subject	Major
Study Procedures criteria	Unscheduled visit not conducted due to AD medication change, or conducted after AD medication change occurred.	Major
Study Procedures criteria	Study MRIs not conducted within study visit schedule.	Minor
Study Procedures criteria	Study MRIs missed	Major
Study Procedures criteria	Administration of rating scales over the telephone.	Minor
Study Procedures criteria	Missed MOCA at an Unscheduled MRI visit.	Major
Study Procedures criteria	Missed MOCA at Day 1 Visit.	Minor
Study Procedures criteria	Missed physical exam, neurological exam, or ECG at study visit.	Minor

CONFIDENTIAL

The information contained herein may not be used, disclosed, or published without the written consent of Biogen MA Inc.

Study Procedures criteria	Missed PET scan at timepoints for PET substudy subjects.	Major
Study Procedures criteria	Ligand dose administration error	Major
Study Procedures criteria	Infusion conducted prior to receipt and review of MRI central read results	Case by case
Visit Schedule Criteria	Study visit or procedures conducted out of window. Please note special attention to the ADCS-ADL-MCI, ADAS-Cog, and NPI at Screening Visit 2 being conducted within 14 days of Screening Visit 1.	Minor
Visit Schedule Criteria	Occurrence of randomization outside of 60-day screening window without sponsor approval.	Minor
Visit Schedule Criteria	Occurrence of randomization outside of 90 days.	Major

